10.2 SAMPLE SIZE CONSIDERATIONS

95% Confidence intervals (CI) for sensitivity and specificity evaluate how precisely sensitivity and specificity have been estimated. The width of CI is dependent on the sample size. 100 TB cases in the final point of care test evaluation (test set), would result in a CI of 85 to 95% for a target sensitivity of 90% (as obtained in the AE-TBC study), based on the binomial distribution. As we expect that about one third of those screened for TB, will be diagnosed with TB, we will aim to recruit 300 participants into this test set. In order to provide for the training set that will be utilized during phase 1 and 2 of this study, we will recruit 500 participants into the training set, for a total of 800 participants recruited for this study.

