4.2 EVALUATION OF TB DIAGNOSIS

An outcome classification committee will classify each participant according to the standard case definitions below. The committee will consist of clinician investigators from the participating sites. They will assign a classification of Definite TB, Probable TB, Possible TB or non-TB (see table below) to each participant, as soon as possible after the week 8 follow up time point. Participants started on TB treatment at clinics will be followed up for 6 months to evaluate treatment response. During phase 3 of the study, the committee will remain blind to the point of care TransDot test results on the test cohort, until outcome classification is complete.

| Pos = positive; neg = negative; con = contaminated; GR = good response; PR = poor response; NG = none given | | | | | | | | | |
|---|--------------------|----------------------------------|------------|-----------------|----------|-------------------|--------------|------------------------|----------|
| Category | Culture | GeneXpert | AFB smear | CXR | Symptoms | TB Treatment | TB Treatment | Response to antibiotic | Class |
| | | | | | | started by clinic | response | (AB), if prescribed | |
| Α | pos | | | | pos | | | | Definite |
| В | neg or con | pos (no TB in past year) | | | pos | | | | Definite |
| С | neg or con | neg or pos (TB in past year) | pos | pos | pos | yes | GR | | Definite |
| D | neg or con | neg or pos (TB in past year) | pos | neg | pos | yes | GR | | Probable |
| E | neg or con | neg or pos (TB in past year) | neg | pos | pos | yes | GR | | Probable |
| F | neg or con | neg or pos (TB in the past year) | neg | pos | pos | No | | PR | Possible |
| G | neg or con | pos (TB in past year) | neg | neg | pos | yes | GR | | Possible |
| н | neg | neg | neg | pos | pos | no | | GR | No TB |
| I | neg | neg | neg | neg | pos | no | | NG | No TB |
| 1 | Not done or con | Not done | Not done | | | | | | Exclude |
| К | Not done or con | pos (TB in past year) | pos or neg | neg or not done | pos | yes PR | | | Exclude |
| L | Not done or contam | Pos TB in past year | pos or neg | neg or not done | pos | no | NG | PR | Exclude |

The case definitions will be applied as shown in the table below:

Definitions:

TB symptoms or signs: symptoms volunteered or specifically elicited by interviewer and signs objectively observed by examiner that include

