For test set participants, serum will be collected for local laboratory based TransDot tests. POC TransDot tests will also be performed on fingerprick blood by the research nurse in a standardized manner across sites, at the baseline visit and before any results from the composite gold standard tests are available. A drop of blood will be applied to the test strip and the test strip will be submitted to the reader. The reported result will be recorded in the case report form. Agreement between the laboratory based and point of care TransDot tests will be calculated. Study investigators will be blinded to the TransDot test results until the final outcome classification has been completed for each participant. TransDot test results will also not be shared with clinic staff and no clinical decisions will be made based on TransDot test results.

A TransDot test will also be done at weeks 8 and 24 to investigate the utility of the test for monitoring treatment response as a secondary outcome. It will be compared to week 8 and 24 treatment outcomes as defined by sputum results, radiology, where applicable and TB symptoms.

It is expected that approximately one third of the participants will have a final diagnosis of active TB, whereas the non-TB cases will have a range of conditions including viral and bacterial lower respiratory tract infections and non-infectious conditions like chronic obstructive pulmonary disease.

The decision to treat for TB and the administration of treatment will remain the responsibility of the national healthcare system, although all relevant results to aid the decision will be shared with clinic staff. Referrals to the appropriate level of care for any accidental discoveries of other conditions or positive HIV results will also be done by the research team.

Participants at Stellenbosch University will receive R150 for participation in the study to compensate for travel expenses and loss of hours at work.

6.2 STUDY SCHEDULE:

Baseline visit (all participants)

Obtain written informed consent. Assign unique study participant ID. Conduct TB symptoms questionnaire. Obtain relevant medical history. Perform directed physical examination. Collect sputum samples for smear (except if results are obtainable from the government clinic), GeneXpert, MGIT culture and storage. Perform chest x-ray.

Perform pre- and post-test counselling for HIV test, except in participants who disclose their known positive status to study nurses.

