10. STATISTICAL CONSIDERATIONS

10.1 STUDY OUTCOME MEASURES AND ANALYSIS

The main outcomes of interest are sensitivity and specificity of the point of care TransDot test during phase 3 of this study. Sensitivity will be calculated as the proportion of true positives (as determined by the composite gold standard of TB case definitions), who test positive on the TransDot test. Specificity will be calculated as the proportion of true negatives who test negative on the TransDot test.

For the primary analysis, the true positives as determined by the composite gold standard of TB case definitions, will consist of the Definite and Probable TB classes. The Possible TB class will be excluded as their diagnosis may involve a significant amount of uncertainty. This group will be included in a secondary analysis to show the TransDot test's performance in this uncertain group of participants.

Secondary outcomes of interest are positive and negative predictive values of the TransDot test, which will be calculated as the proportion of participants with positive or negative tests who are positive or negative according to case definitions, respectively.

Sensitivity, specificity, positive and negative predictive values will be reported with 95% confidence intervals.

Reproducibility of the test will be determined between laboratory based tests and point of care tests, as well as between the point of care tests conducted in the different countries, using the Kappa statistic for agreement.

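### Section 10.2 gives a 95% CI of 85 to 95% for 90% sensitivity in 100 TB cases; no standard 95% binomial method gives this, and the exact interval is 82.4 to 95.1%

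*Combined protocol and SAP*

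**What the plan says.** Section 10.2 (Sample Size Considerations) opens by fixing the confidence level: "95% Confidence intervals (CI) for sensitivity and specificity evaluate how precisely sensitivity and specificity have been estimated". It then gives its one precision figure: "100 TB cases in the final point of care test evaluation (test set), would result in a CI of 85 to 95" percent, "for a target sensitivity of 90% (as obtained in the AE-TBC study), based on the binomial distribution". Because about one third of those screened are expected to have TB, the section concludes: "we will aim to recruit 300 participants into this test set".

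Section 10.1 (Study Outcome Measures and Analysis) uses the same level for the analysis: "Sensitivity, specificity, positive and negative predictive values will be reported with 95% confidence intervals". It names no interval method. For the primary analysis it counts the Definite and Probable classes as TB and adds: "The Possible TB class will be excluded as their diagnosis may involve a significant amount of uncertainty". The case-definition table in section 4.2 also contains rows that remove a participant altogether, for example "Not done or con | Not done | Not done | | | | | | Exclude". Section 6.1 repeats the prevalence assumption: "It is expected that approximately one third of the participants will have a final diagnosis of active TB".

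**The concern.** An interval of 90% plus or minus 5 points looks too narrow for 100 observations at the 95% level. The standard error of a proportion of 0.9 with n = 100 is 3 points, so 1.96 standard errors is 5.9 points. Limits set only 5 points away on each side imply either a lower confidence level or a larger sample.

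The sentence matters because the size of the test set rests on it: 100 cases divided by one third gives 300 participants. Sensitivity on fingerprick blood is a primary outcome, and section 4 sets 90% or above as the sensitivity aim for optimising the test. A funder, ethics committee or reader of section 10.2 would take it that an observed 90% rules out sensitivities below 85%. With 100 cases it does not.

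**Working it through.** **Inputs.** Confidence level 95% (sections 10.1 and 10.2); n = 100 TB cases and sensitivity 0.90, so x = 90 (section 10.2); test set of 300 and prevalence of about one third (section 10.2).

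**Step 1: try to reproduce 85 to 95%.** By the normal approximation,

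SE = √(0.9 × 0.1 / 100) = 0.030

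95% limits = 0.90 ± 1.96 × 0.030 = 0.90 ± 0.0588, which is 84.1 to 95.9%.

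The exact Clopper-Pearson limits are the 2.5th percentile of Beta(x, n − x + 1) = Beta(90, 11) and the 97.5th percentile of Beta(x + 1, n − x) = Beta(91, 10), which gives 82.4 to 95.1%.

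Common methods for 90/100 at the 95% level:

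| Method | Lower % | Upper % |
|---|---|---|
| Clopper-Pearson (exact) | 82.4 | 95.1 |
| Mid-P | 82.9 | 94.8 |
| Wilson | 82.6 | 94.5 |
| Agresti-Coull | 82.4 | 94.7 |
| Jeffreys | 83.0 | 94.7 |
| Normal approximation | 84.1 | 95.9 |
| *Stated in section 10.2* | *85* | *95* |

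Six further variants (continuity-corrected Wald and Wilson, inverted exact test, logit, arcsine, likelihood ratio) have lower limits between 82.0 and 83.4%. None of the twelve rounds to 85 to 95.

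**Step 2: look for an explanation.**

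- *Different confidence level.* A half-width of 5 points means z = 0.05 / 0.03 = 1.667, and 2Φ(1.667) − 1 = 0.904. The 90% normal-approximation interval is 85.1 to 94.9%, which rounds to the stated figures. The 5th and 95th percentiles of a Binomial(100, 0.9) count are also 85 and 95.
- *A range for the observed count rather than a CI.* The 2.5th and 97.5th percentiles of Binomial(100, 0.9) are 84 and 95. The range 85 to 95 holds 93.6% of the distribution.
- *The 89% sensitivity reported in section 2.2.* For 89/100 the 95% interval is 81.2 to 94.4% (exact) or 82.9 to 95.1% (normal approximation). This does not recover 85 to 95 either.

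**Step 3: size of the discrepancy.**

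- Lower limit: 85 − 82.4 = 2.6 points (exact); 85 − 84.1 = 0.9 points (normal approximation).
- Width: 95.1 − 82.4 = 12.7 points (exact) or 95.9 − 84.1 = 11.8 points (normal approximation), against 10 stated.
- Cases that a 95% normal-approximation half-width of 5 points would need: 1.96² × 0.09 / 0.05² = 138.3, so 139 cases, or 139 × 3 = 417 participants at one third. This only scales the gap; it is not a request to enlarge the trial.

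**Step 4: is 100 the right denominator?** 300 × 1/3 = 100 is consistent but leaves no margin. With exactly one third, the number of cases among 300 is Binomial(300, 1/3), and P(fewer than 100) = 0.478. The documents give no expected share for the Possible class or the Exclude rows, so the following evaluable numbers are assumed for illustration, each with 90% observed and exact limits:

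| Cases | Positives | 95% CI % |
|---|---|---|
| 100 | 90 | 82.4 to 95.1 |
| 90 | 81 | 81.9 to 95.3 |
| 80 | 72 | 81.2 to 95.6 |

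**The case against.** The arithmetic itself is hard to dispute, but there are fair points about how much it matters.

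First, the stated limits do have a standard counterpart at the 90% level. That is a plausible source and it stands as an explanation. It does not rescue the sentence, because section 10.2 introduces its intervals as 95% and no other level appears anywhere.

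Second, the size of the error depends on the comparator. Clopper-Pearson is a conservative choice; under the normal approximation each limit is off by only 0.9 points, and the exact upper limit (95.1%) agrees with the stated one. The reference to the binomial distribution does not by itself name the exact method. This stands, so the error is best given as a range.

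Third, the shortfall argument is secondary. Any plan built on an expected count has roughly an even chance of falling short. It is also unsettled whether the one third already leaves out Possible cases: section 2.2 reports one third with confirmed TB in the earlier project, but the documents do not say that this is the source of the planning figure. The effect is small in any case, since 80 cases instead of 100 moves the exact lower limit from 82.4 to 81.2%. This would not be worth raising alone.

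Fourth, no hypothesis test, success threshold or go/no-go rule is tied to an 85% lower limit, and the reported intervals will come from the data. That is correct and limits the consequence to the planning statement.

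**Conclusion.** The concern holds. With 100 TB cases and 90% observed sensitivity, no standard 95% binomial interval is 85 to 95%. The exact interval is 82.4 to 95.1%. Across the six methods tabulated the lower limit runs from 82.4 to 84.1%, so the stated limit is 0.9 to 2.6 points too favourable. A half-width of 5 points at this sample size carries about 90% confidence.

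This rests only on the section's own inputs (100 cases, 90%, 95% level). The figures for 80 and 90 cases rest on assumed evaluable numbers and are illustrative. The error should be fixed because it is the sole stated precision for the 300-participant test set. It does not bias any result or change the planned analysis.

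**What to change.** In section 10.2, replace the precision sentence with one such as: *With 100 Definite or Probable TB cases and an observed sensitivity of 90%, the exact (Clopper-Pearson) 95% CI is 82.4 to 95.1%.*

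In section 10.1, name the interval method for the final analysis and keep it the same as in section 10.2. Clopper-Pearson fits the reference to the binomial distribution; another named method, such as Wilson, would also serve provided the figure in section 10.2 is changed to match (82.6 to 94.5%).

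Optionally, add an illustrative sentence that with 90 or 80 evaluable cases the exact interval would be 81.9 to 95.3% or 81.2 to 95.6%, and say whether the assumed one third counts Possible cases.

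The cost is one sentence in section 10.2 and a few words in section 10.1. The only drawback is a slightly less favourable stated precision; enrolment and procedures are unchanged.

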However, a promising serum host inflammatory signature was identified during this project after investigation of more than 70 serum host inflammation markers, including acute phase proteins, T helper cell 1, T helper cell 2 and regulatory cytokines, soluble cytokine receptors and growth factors. The original set of markers for screening were chosen according to the availability of multiplexed assays (Luminex platform) and their known roles in inflammation and represented a wide spectrum of markers with diagnostic potential. The most promising host serum protein signature was subsequently validated on 687 people from five African countries with suspected TB, regardless of HIV infection status or ethnicity, providing the basis for the follow-up work suggested herein. The six-analyte signature of C-reactive protein (CRP), Interferon gamma (IFN-γ), pre-albumin, complement factor H (CFH), apolipoprotein A1 and inducible protein 10 (IP-10) ascertained TB disease with a sensitivity of 89% (CI 78 – 95%) and specificity of 76% (CI 68 – 83%), (positive predictive value of 61%; negative predictive value of 94%) ([7], [8]). Measurement of multiple markers and evaluation of their ratios offset a lack of disease specificity of individual markers. These performance characteristics would constitute a valuable screening test if converted into an inexpensive POC test and would prioritize individuals with a high likelihood of active TB for confirmatory testing by GeneXpert.

During the AE-TBC project, partner Leiden University Medical Centre (LUMC) developed and validated a user-friendly lateral flow assay (LFA) for simultaneous detection of multiple host TB biomarkers (cytokines and antibodies) in blood or other body fluids [9, 10]. These LFAs are likely to assist in rapid TB diagnosis in low-resource settings and were tested in the AE-TBC field sites. Importantly, our test formats utilize novel, nano-sized upconverting phosphor (UCP) reporter particles as read-out [11, 12, 13]. The UCP-technology delivers flexibility with respect to sensitivity and robustness as the ultrasensitive fluorescent label is not hampered by common auto-

fluorescence background. Moreover, the label does not fade, allowing UCP-test strips to be stored indefinitely for reanalysis. The LFA can also be modified for measurement of markers in fingerprick blood, which will further enhance its POC utility.

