11.3 INFORMED CONSENT PROCESS

Obtaining informed consent is a process rather than an event and discussions to ensure participant understanding and continued willingness to participate should take place at every study visit.

No trial activities will take place before the informed consent form has been signed by a participant or before the respective ethical review boards have given permission for the study. A research nurse will discuss the purpose, duration, procedures, alternatives, risks and benefits of the study with potentially eligible participants. The potential participant will be given the opportunity to ask questions or discuss the

study with family members before signing the consent form. The nurse conducting the discussion will also ask the participant questions to assess the participant's understanding.

People who are not able to give informed consent for themselves, will not be included in this study. At Stellenbosch University the informed consent discussion will be conducted in English or Afrikaans, according to the preference of the participant. In the case of Xhosa speaking participants, an interpreter could be used to translate English or Afrikaans to Xhosa. Informed consent forms will be available in English, Afrikaans and Xhosa. The language used will be documented in the participant file. In the case of a participant who cannot read and write, an independent witness will be present during the discussion and will sign in addition to the participant's thumbprint. This will also be documented in the participant file.

The participant may withdraw consent at any stage and will be informed that withdrawal will not influence their routine clinical care.

A participant may also be withdrawn from the study at the discretion of the study investigators if their further participation is somehow deemed to be a risk to their safety or if lack of the participant's cooperation compromises the quality of the study.

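### Section 10.2's 100 TB cases are an expected count with no allowance for unclassifiable participants, and 100 cases do not give the stated 95% interval of 85 to 95%

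*Combined protocol and SAP*

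**What the plan says.** The only numerical case for the size of the test set is in section 10.2. It states that "100 TB cases in the final point of care test evaluation (test set), would result in a CI of 85 to 95"%. The sensitivity assumed there is 90%. The section cites the binomial distribution but does not say which interval method was used, and it introduces the limits as 95% confidence limits. It then divides by the expected TB share to reach a head count: "As we expect that about one third of those screened for TB, will be diagnosed with TB, we will aim to recruit 300 participants". Recruitment is defined by head count elsewhere too: section 5.1 stops at about 800 people overall, and section 6.1 opens the test cohort once 500 are in the training cohort.

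Section 10.1 restricts the positives in the primary analysis to the Definite and Probable classes. "The Possible TB class will be excluded as their diagnosis may involve a significant amount of uncertainty"; that group appears only in a secondary analysis.

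The case-definition table in section 4.2 matters in three ways:
- Rows A and B (Definite) rest on symptoms plus a positive culture, or on symptoms plus a positive GeneXpert with no TB in the past year. Neither row has a follow-up entry.
- Rows C to E (Definite or Probable) require that treatment was started and a good response seen. The definitions below the table judge response after at least two months of treatment.
- The last three rows are classed Exclude.

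No expected share is given for Possible, for Exclude, or for participants lost before classification.

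**The concern.** The step from 100 cases to 300 recruits has no margin, while the plan itself provides ways for a recruit not to become a primary-analysis case. If some expected cases drop out of the Definite and Probable classes, the primary sensitivity estimate rests on fewer cases than section 10.2 states, and no rule restores the number. The interval quoted in the same sentence also looks too narrow for 100 cases. Since this sentence is the whole justification for the test set, both the count and the precision need to be figures that the design can deliver.

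**Working it through.** **Inputs.** Section 10.2: 300 recruits, TB share 1/3, 100 cases, sensitivity 90%, 95% confidence (taken as two-sided). Section 10.1: positives are Definite plus Probable. The share *d* of expected primary cases that is lost is not in the documents, so it is an assumption shown as a range.

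**1. The plan's case count.** 300 × 1/3 = 100, or equivalently 100 ÷ (1/3) = 300. The figure reproduces exactly, with no inflation term.

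**2. What 100 means with no loss.** Treat the number of cases as binomial with n = 300 and p = 1/3. The mean is 100, the SD is √(300 × 1/3 × 2/3) = 8.2, and the central 95% range is 84 to 116. P(at least 100 cases) = 0.52.

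**3. The plan's interval.** The Wald 95% half-width at 90/100 is 1.96 × √(0.9 × 0.1/100) = 0.0588. No standard 95% method gives 85 to 95%:

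| Method, 90/100 | 95% interval |
|---|---|
| Wald | 84.1 to 95.9 |
| Exact (Clopper-Pearson) | 82.4 to 95.1 |
| Wilson | 82.6 to 94.5 |
| Agresti-Coull | 82.4 to 94.7 |
| Jeffreys | 83.0 to 94.7 |

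A 90% Wald interval is 85.1 to 94.9, which matches the stated limits after rounding. The documents do not say whether that is their origin. A 95% Wald half-width of 5 points would need 1.96² × 0.09/0.05² = 138.3, so 139 cases, or 139 × 3 = 417 recruits at one third.

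**4. Effect of loss.** Expected cases = 100 × (1 − d). P(at least 100) uses p = (1 − d)/3 with n = 300.

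| Assumed d | Expected cases | P(at least 100) | Exact 95% interval at 90% | Width, points |
|---|---|---|---|---|
| 0 | 100 | 0.52 | 82.4 to 95.1 | 12.7 |
| 5% | 95 | 0.29 | 82.1 to 95.2 (85.5/95, a notional count) | 13.1 |
| 10% | 90 | 0.12 | 81.9 to 95.3 | 13.5 |
| 20% | 80 | 0.01 | 81.2 to 95.6 | 14.3 |

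**5. Which routes of loss reduce the 100.**
- Exclude rows, where the person would otherwise have counted within the one third.
- Cases that could be classed only through rows C to E and are lost before a treatment response can be judged.
- Possible, but only if the one third includes it. Section 2.2 uses one third for confirmed active TB in the earlier study. Section 6.1 uses it for a final diagnosis of active TB. Section 10.2 uses it for people diagnosed with TB. None maps it to the classes. If it means Definite plus Probable, Possible participants come from the other two thirds and reduce the specificity denominator instead.

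**The case against.** The strongest reply is that the effect is small and uncertain. The TransDot test, sputum tests and chest X-ray are done at baseline, and rows A and B need nothing later, so a withdrawal after baseline need not cost a case. The Exclude rows are narrow. The one third is approximate, and with no loss the count could fall anywhere from 84 to 116. No loss rate has a source in the documents, and even 20% widens the exact interval only from 12.7 to 14.3 points. All of this stands. It limits the size of the point, but it does not supply the missing allowance or rescue the 85 to 95% interval.

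Three stronger readings are tempting, and the documents do not support them.

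- A reader might infer that 100 cases are reached only if no one withdraws, is classed Possible or is excluded. Rows A and B, the undefined one third and chance variation in the case count each defeat that.
- A reader might infer from section 2.2 ("positive predictive value of 61%; negative predictive value of 94"%) that the true TB share is about 30%. With sensitivity 89% and specificity 76%, the PPV gives 0.61 × 0.24/(0.89 × 0.39 + 0.61 × 0.24) = 0.297, and the NPV gives 0.306. These inputs are rounded: rounding alone spans 28.7 to 30.7% from the PPV and 27.6 to 33.6% from the NPV. The sensitivity interval of 78 to 95% fits roughly 60 to 70 cases, far fewer than 30% of 687 (about 206), so the figures appear to describe a subset. They do not displace the one third that the same section reports for more than 1,300 people.
- A reader might infer from section 11.3 ("A participant may also be withdrawn from the study at the discretion of the study investigators") that withdrawn people's baseline data are discarded, or that withdrawal could be steered by the index test. Section 11.3 limits this to safety risk or non-cooperation that harms study quality, and it never says that collected data are dropped. Section 4.2 has the committee classify each participant. Section 6.1 blinds investigators to TransDot results until final classification. A sentence on data retention would be a clarification, not part of this point.

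**Conclusion.** The point holds in a limited form. The sizing in section 10.2 has no allowance for recruits who cannot be classed Definite or Probable and no rule to continue to 100 primary cases. The figure of 100 is therefore at best an expectation, met or exceeded with probability about 0.52 when nothing is lost. Any loss not already netted out of the one third lowers it. That the final analysis will have fewer than 100 cases is not established: a TB share of 37.0% (0.333/0.9) would offset a 10% loss.

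The cost in precision from such loss is modest. The firmer error is the stated interval, which 100 cases do not deliver at 95% confidence by any standard method. The exact lower limit is 82.4%, not 85%. This second finding needs no assumption about loss. The first rests on the plan's own one third, on independent participants for the binomial probabilities, and on loss rates that are assumptions.

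**What to change.** Change section 10.2 only:

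1. Say whether the one third means Definite plus Probable per person recruited, or also includes Possible.
2. Restate the expected number of primary-analysis cases from 300 recruits under stated loss assumptions, labelled as such: for example 95, 90 or 80 cases at 5, 10 or 20% loss.
3. Replace 85 to 95% with the matching 95% interval and name the method. With the exact method this is 82.4 to 95.1% at 100 cases, 81.9 to 95.3% at 90 and 81.2 to 95.6% at 80.

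This is a wording change and needs no extra participants. The downside is a slightly less favourable stated case number and precision.
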